#### ***b. Patient Selection and Inclusion/Exclusion Criteria***

Study-trained staff will screen and recruit eligible patients. All NICU admissions will be screened for potential eligibility. The NICU attending physician will be informed of any patient who meets eligibility criteria and he/she or a designee will be asked to make an introduction of study staff to the parents/guardians. The goal will be for patients to be recruited within 24 hours after criteria for hypoglycemia has been met.

##### **Inclusion Criteria:**

- Age: 0-60 days old
- Gestational Age: > 33 6/7 weeks gestational age (late-preterm and term)
- Hypoglycemia: two episodes of hypoglycemia >1 hour apart (hypoglycemia will be defined by age: <48 hours of life <50mg/dL and >48 hours of life <70mg/dL)

##### **Exclusion Criteria:**

- Diffuse skin disease such that placement of a CGM sensor would be difficult to secure
- Infants colonized or infected with multi-drug resistant organisms (i.e. MRSA, VRE, ESBL producing bacteria)
- Patients on hypothermic protocols
- Expected to remain in NICU <24 hours
- Enrolled in a competing clinical trial
- Family/team have decided to limit or redirect from aggressive NICU technological support
- Ward of the state

#### ***Description of Study Treatments or Exposures/Predictors***

Continuous Glucose Monitors (CGMs) will be placed in all enrolled patients. CGMs measure glucose concentration in the interstitial fluid of the subcutaneous space every few seconds and report average blood glucose levels approximately every 5 minutes. CGMs have 3 components: a glucose sensor, a transmitter, and a receiver. The glucose sensor is inserted subcutaneously with a 26-gauge introducer needle and remains in place under the surface of the skin for up to 7 days. The sensor’s platinum tip is embedded with glucose oxidase enzyme, which catalyzed a reaction whereby electrical current is generated which is proportional to ambient glucose concentration. The current is then measured and translated into a glucose reading once it is wirelessly sent by the transmitter to the small hand-held receiver. The receiver then displays the glucose level in mg/dL and can alert at specified glucose levels.

*c. Definition of Primary and Secondary Outcomes*

This is a pilot study to determine the feasibility of using CGMs to improve short term outcomes of neonates with hypoglycemia. Planned comparisons for a larger study will be powered from the data obtained. The primary endpoint will be a reduction in incidence and severity of hypoglycemia in infants on the CGM Protocol. Secondary outcomes will include reduction in in time-to-diagnosis, time-to-treatment initiation and time-to-euglycemia on a sustainable feeding regimen.

*d. Data Collection Methods, Assessments and Interventions*

- *Data collection:*

When a subject is first enrolled we will collect demographic Information (age at diagnosis of hypoglycemia, gestational age at birth, sex) as well as physical characteristics (weight and body surface area). Once a subject is on a CGM, the CGM glucose data will be downloaded onto a research team computer and reviewed daily. Laboratory results (including blood glucose levels and critical sample results (ketones, insulin, cortisol, growth hormone, fatty acids, total and free carnitine, plasma amino acids, urine organic acids, lactic acid, pyruvate), brain imaging and EEG readings, all intravenous and enteral sources of glucose, other sources of nutrition, hypoglycemia therapeutic interventions (eg. glucagon, diazoxide, octreotide, corticosteroids and carnitine replacement) as well as underlying etiology of hypoglycemia and other associated diagnoses will be reviewed and collected every 2-3 days.

- *Assessments:*

The CGM site will be evaluated daily to assess for any signs of bleeding or infection. CGM readings will be downloaded to a study team computer once a day. The CGM data will be reviewed daily to ensure the CGM monitor is functioning properly, being calibrated appropriately and to assess whether any episodes of severe unrecognized hypoglycemia have occurred.

- *Interventions:*

Subjects in the study will have a continuous glucose monitor (CGM) placed in one of their thighs. A numbing cream will be used before the CGM is inserted to reduce pain. The CGM has a small plastic catheter with a needle in it. It comes with an insertion device which pushes the catheter under the skin. The needle is then removed, so only the catheter stays under the skin with the device on top of it. After the CGM is placed, two blood glucose levels will be obtained (usually by heel prick) so that the device can be calibrated. Afterwards at least two blood sugar levels need to be obtained every day so that the CGM can continue to work properly. Infants with hypoglycemia need to have their blood glucose monitored routinely, so on most days no extra blood glucose sampling will be required as we will use the values obtained by the NICU team. Additional blood glucose levels may need to be obtained if the CGM reports current or impending hypoglycemia. All non-CGM monitoring and management decisions will be at the discretion of the NICU team. The CGM may need to be replaced in case of a sensor dislodgement or malfunction, or if it has been in place for more than 7 days. Live CGM glucose values will be available to the medical team in the “CGM protocol” group. Additionally the medical team will be provided print outs of the CGM data on a daily basis for the “CGM protocol” group. CGM data from patients in the “Standard of Care” group will also be reviewed daily. Notification will occur immediately following identification of three unrecognized severe episodes of hypoglycemia. Given that the CGM data will be analyzed daily, this will at most be 24 hours (although most likely less than 24 hours) after the event occurred.

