**1. Specific Aims and Objectives**

We seek to improve the management and outcome of neonates diagnosed with hypoglycemia. We hope to accomplish this by using continuous glucose monitors (CGMs) in at-risk infants admitted to the neonatal intensive care unit (NICU). Current management of neonatal hypoglycemia involves intermittent blood sampling, which, unlike CGMs, does not offer real-time blood glucose trends and therefore leaves infants at risk for unrecognized hypoglycemia. Unrecognized hypoglycemia may not only lengthen time to diagnosis and appropriate treatment, but may also lead to poor neurodevelopmental outcomes. Our long-term goal is to assess whether use of CGMs can improve clinical course and outcomes in this population. This pilot study will allow us to test whether it is feasible to perform in larger-scale the proposed randomized, controlled trial comparing a “CGM Protocol” group and a “Standard of Care” group to assess whether use of CGMs in neonates can:

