**c) Reduce the time taken to achieve stable euglycemia on a sustainable feeding regimen.**

*Hypothesis: CGMs will shorten time to achieving a stable, normal blood glucose concentration on a sustainable feeding regimen.*

By performing a pilot study we hope to test the feasibility of our study design. We plan to use the results to assess the validity of our chosen outcome measures, inform power and sample size considerations and test the practicality of our study timeline for larger-scale study on the same topic. The results of this study could potentially alter the way neonatal hypoglycemia is routinely managed and thereby improve neurodevelopmental outcomes in this population.

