Infants will be randomized to a "CGM Protocol" or a "Standard of Care" group. We aim to enroll ten patients in each study arm. Those on the CGM Protocol will have a fully accessible CGM that will be analyzed in real-time for blood glucose trends and will alarm for any blood glucose level approaching hypoglycemic threshold. The CGM alarm will sound if blood glucose is less than 60 mg/dL for all patients. The CGM will also alarm if the rate of drop in blood glucose is greater than 20 mg/dL/minute and thus concerning for impending hypoglycemia. These thresholds are programmed into the CGM by a study team member and will not be modifiable by the medical team. Those in the "Standard of Care" group will have a CGM in place but live readings will not be available to the clinical team. However, the research team will review CGM data from the "Standard of Care" group daily and if a subject in the "Standard of Care" group has three episodes of unrecognized severe hypoglycemia (eg. BG <40 mg/dL), the study team will alert the NICU providers. Notification will occur immediately following identification of the third unrecognized severe episode of hypoglycemia, which will at most be 24 hours after the event occurred.

For subjects in the "CGM Protocol" group, whenever the CGM alarms or there is a concerning blood glucose trend according to the CGM, the nurse will be asked to check a blood glucose value. All clinical

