## 9. Statistical Power and Sample Considerations

This is a feasibility study and therefore is not powered; however, the choice of 10 subjects in each of two groups is generally considered acceptable for feasibility/pilot studies and should allow the variance in the primary outcome (decrease in frequency and severity of hypoglycemia with use of CGMs) to be formally assessed for use in a subsequent larger study.

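### A declared feasibility pilot has an efficacy primary endpoint and no pre-specified feasibility outcome or criterion for going on to the larger trial

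*Combined protocol and SAP*

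**What the plan says.** The purpose is stated four times. Section 1 says: "This pilot study will allow us to test whether it is feasible to perform in larger-scale the proposed randomized, controlled trial". The end of that section adds "By performing a pilot study we hope to test the feasibility of our study design". It lists three uses of the results: judging the outcome measures, informing power and sample size, and to "test the practicality of our study timeline for larger-scale study on the same topic". Section 4c opens with "This is a pilot study to determine the feasibility of using CGMs to improve short term outcomes of neonates with hypoglycemia", and Section 9 says "This is a feasibility study and therefore is not powered".

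The endpoint is stated once, in Section 4c: "The primary endpoint will be a reduction in incidence and severity of hypoglycemia in infants on the CGM Protocol". The secondary outcomes are time-to-diagnosis, "time-to-treatment initiation and time-to-euglycemia on a sustainable feeding regimen". Section 8 assigns a chi-squared test to incidence and the Mann-Whitney test to time-to-diagnosis and time-to-euglycemia. Severity is to be compared, but no test or summary is named for it. On size, Section 4a says "We aim to enroll ten patients in each study arm".

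Some feasibility-type information is also planned. Section 8 calculates the mean absolute relative difference (MARD) between sensor and blood glucose, Section 5 has enrolment reviewed monthly, Section 7 keeps a deviation log, and Sections 4a and 4b set a goal of recruiting within 24 hours of meeting the hypoglycemia criteria.

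**The concern.** The outcomes and tests do not line up with the main declared purpose. A reader who wants to know whether the larger trial can be run will find no named measure of recruitment, usable sensor time, response to alarms or completeness of outcomes, and no statement of what result would support going ahead. The formal output would be between-arm tests on a question that Section 9 says the trial is not powered to answer. The decision on the larger trial would then have no agreed basis, although the data needed for one are largely within reach.

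**Working it through.** **Step 1. Declared goals set against what is specified.**

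| Goal (Section 1) | What the plan specifies | Outcome or limit set? |
|---|---|---|
| Feasibility of the design | Deviation log (Section 7), MARD (Section 8) | Neither |
| Validity of the outcome measures | Nothing beyond the comparisons themselves | Neither |
| Power and sample-size inputs | Hypoglycemia by arm (Sections 4c, 9) | Outcome yes, but Section 8 has no variance-estimation step |
| Practicality of the timeline | About 18 months (Section 4e), monthly enrolment review (Section 5) | Neither |

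The timeline implies 20/18 = 1.11 infants per month. No minimum rate is stated.

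**Step 2. What the planned incidence test can show.** Ten per arm is justified by convention, without a formula, so there is no calculation to reproduce. Inputs: n = 10 per arm (Sections 4a, 9) and a chi-squared test (Section 8). The documents give no significance level, sidedness or event rates, and do not say whether incidence means the share of infants with at least one event. I assume that it does, with a two-sided 5% level and a range of rates.

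Exact power = Σx Σy Bin(x; 10, p1) · Bin(y; 10, p2) · I[p-value(x, y) < 0.05], summed over all 11 × 11 possible tables.

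| Assumed rates | Pearson | Fisher |
|---|---|---|
| 90% vs 60% | 29% | 15% |
| 90% vs 70% | 14% | 6% |
| 50% vs 25% | 18% | 9% |
| 90% vs 30% | 82% | 67% |

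An example: observing exactly 9/10 versus 6/10 gives χ² = 20 × (9×4 − 1×6)² / (10 × 10 × 15 × 5) = 18,000/7,500 = 2.4, below the 5% critical value of 3.84.

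**Step 3. The ceiling.** Section 4b requires two hypoglycemic episodes before entry, so having at least one further event may be close to universal. That is an inference; no rate is given.
- With 10/10 versus 7/10, χ² = 20 × (10×3 − 0×7)² / (10 × 10 × 17 × 3) = 18,000/5,100 = 3.53, p = 0.06 (Fisher 0.21).
- With 10/10 versus 10/10, the no-event column is zero and the statistic is undefined.

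**Step 4. What 20 infants can say about feasibility.** Clopper-Pearson 95% limits for x of n are the 0.025 quantile of Beta(x, n−x+1) and the 0.975 quantile of Beta(x+1, n−x). The counts are illustrative.
- 18/20: 68% to 99%
- 16/20: 56% to 94%
- 8/10 (CGM Protocol arm only): 44% to 97%

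These intervals are wide, but they can be read against a limit fixed in advance. They apply only where each infant contributes one yes or no.

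**Step 5. What 20 infants can say about variance.** Take a continuous per-infant measure, assumed normal with a common SD, on 18 degrees of freedom. The variance multiplier runs from 18/31.53 = 0.57 to 18/8.23 = 2.19, so the SD runs from 0.76 to 1.48 times its estimate. A sample size proportional to the variance then spans 2.19/0.57, about 3.8-fold.

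**The case against.** The strongest reply is that hypoglycemia by arm is a proper thing for this pilot to measure. Section 4c says that the larger study will be powered from these data, Section 9 gives variance as the reason for ten per arm, and Section 4a states an efficacy aim outright. The purposes are mixed, and the lack of power is openly declared. All of this stands. It limits the point to what is missing and to the use of hypothesis tests; it is no argument for a larger sample.

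Three stronger readings are tempting, and the documents do not support them.
- *That the plan gives no answer on feasibility.* MARD, the monthly enrolment review, the deviation log and the 24-hour recruitment goal would all yield information. What is absent is a pre-specified outcome and a criterion.
- *That the primary endpoint is unrelated to the trial's purpose.* It serves the sample-size aim, if loosely: incidence and severity are not one variable, and the variance would be imprecise (step 5).
- *That a null test would end the programme, or a chance positive would be taken as proof.* No significance level and no decision rule based on a p-value is stated, so this is conjecture.

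It can also be said that fixed progression limits are only one accepted way to run a pilot. That is fair, but Section 1 promises to test feasibility, and some stated basis for judging it is needed.

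**Conclusion.** The point holds in a limited form. The trial declares a feasibility aim, makes an efficacy reduction primary, tests efficacy between arms, and defines neither a feasibility outcome nor a result that would support the larger trial. For moderate assumed differences the planned chi-squared test has power of 14% to 29% (6% to 15% with Fisher). About 80% power needs a fall as large as 90% to 30%, and the test cannot be computed if every infant has an event. The power figures rest on an assumed two-sided 5% level, assumed rates and a per-infant reading of incidence. The mismatch itself rests on the text alone. The sample of 20 is not the fault.

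**What to change.** **Section 4c.** Name feasibility outcomes as primary and set a progression limit for each before enrolment. For example:
- the share of eligible infants randomised within 24 hours of meeting the criteria;
- usable, calibrated sensor time per infant;
- the share of CGM Protocol alarms followed by a blood glucose check;
- the share of infants in whom each efficacy outcome could be determined.

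Use exact binomial 95% intervals only for per-infant proportions, with the right denominator: eligible infants for the first, the 20 randomised for the last. Sensor hours and alarms are clustered within infants, and alarms arise in the CGM Protocol arm only. Summarise these per infant, or use a method that allows for clustering.

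**Section 8.** Report incidence, severity and the time outcomes as secondary or exploratory estimates by arm, with 95% confidence intervals and the variance estimates needed for planning. State that no efficacy conclusion will be drawn from p-values.

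**Cost.** This is a cheap improvement, mostly wording and tabulation. The pilot gives up a primary efficacy claim. The documents describe screening of all admissions and daily sensor downloads, but no log of eligible or refusing families and no recording of alarm times, so a simple screening and consent log and an alarm record may have to be added.

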### *e. Study Timeline*

Subjects will be enrolled ideally within 24 hours of diagnosis of hypoglycemia. The CGM will remain in place until the subject is on a sustainable feeding regimen and no longer having hypoglycemia. The CGM will be removed 24-48 hours after the NICU team has deemed the hypoglycemia resolved or stable enough for its continued management at home. We expect most patients to be in the study for at least a week but duration can vary significantly depending on the etiology of the hypoglycemia and how challenging it is to control. In the event that a patient continues to have unstable hypoglycemia 28 days after randomization into the study, then study participation will conclude on the 28th day and the CGM will be removed at that time. We expect to carry on the study for approximately 18 months.

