management decisions will be made by the clinical team based on laboratory or bedside monitor-confirmed blood glucose values. The CGMs will be calibrated, at a minimum, every 12 hours with a blood glucose value measured by bedside glucometer. Additional calibrations will be performed if more frequent blood glucose monitoring is deemed necessary by the NICU team. In the “Standard of Care” group, the only change to current management is the potential performance of additional blood glucose checks that may be prompted if repeated unrecognized severe hypoglycemia is detected by the research team. The CGM will remain in place until the infant is no longer being monitored for glycemic stability or until the infant is discharged. If hypoglycemia work-up and management lasts longer than a week, the CGM sensor will be replaced on the seventh day after initial insertion. In the case of a sensor dislodgement or malfunction, it would also be replaced. Lastly, if a patient continues to have unstable hypoglycemia for longer than 28 days (eg. four 7-day cycles of CGM) then their study participation will also end at that time.

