## 8. Data Analysis Plan

Hypoglycemia will be defined as a laboratory or bedside monitor blood glucose value of <50 mg/dL prior to 48 hours of life and <70 mg/dL after 48 hours of life or CGM values below threshold for >30 minutes with no concomitant blood sugar reading. Hypoglycemic episodes within one hour of each other will be considered as one event. Severe hypoglycemia will be defined as less than 40mg/dL. Euglycemia will be defined as 48 hours with blood glucose equal or greater than 70mg/dL after 48 hours of life or equal or greater than 50mg/dL if before 48 hours of life.

We will record all blood glucose levels, laboratory data related to the investigation of the underlying cause of hypoglycemia, intravenous and enteral sources of glucose, and other related therapeutic interventions such as administration of diazoxide, octreotide, glucocorticoids, and carnitine. Data analysis will begin by comparing blood glucose data with information from the CGM monitors to assess for accuracy of the CGMs. This will be done by calculating the mean-absolute-relative-difference (MARD) between sensor-measured glucose levels and laboratory or bedside meter-measured blood glucose values. We will then compare the severity and frequency of hypoglycemia, as well as the time to diagnosis and time to euglycemia on a sustainable feeding regimen between the “CGM Protocol” and “Standard of Care” groups. Chi-squared analysis will be used to assess differences in the incidence of hypoglycemia while the Mann-Whitney U test will be used to analyze differences in time-to-diagnosis and time-to-euglycemia.

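### Time-to-euglycemia needs 48 hours at or above threshold, but no section guarantees 48 hours of glucose observation after the last low value, and the analysis has no censoring rule

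*Combined protocol and SAP*

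**What the plan says.** - **Endpoint.** Section 4c lists time-to-euglycemia on a sustainable feeding regimen as a secondary outcome. Section 8 states: "Euglycemia will be defined as 48 hours with blood glucose equal or greater than 70mg/dL after 48 hours of life", with a lower threshold before that age. The definition is written on blood glucose.
- **Hypoglycemia.** Section 8 counts low blood values and also "CGM values below threshold for >30 minutes with no concomitant blood sugar reading".
- **Sensor removal, Section 4e.** "The CGM will be removed 24-48 hours after the NICU team has deemed the hypoglycemia resolved", or "stable enough for its continued management at home".
- **Sensor removal, Section 4a.** "The CGM will remain in place until the infant is no longer being monitored for glycemic stability or until the infant is discharged". This rule has no 24-48 hour tail.
- **Blood samples.** Section 4d requires at least two a day so that the sensor keeps working. It leaves all other monitoring to the NICU team.
- **Entry and exit.** The only exclusion based on length of stay is "Expected to remain in NICU <24 hours". Participation also ends "if a patient continues to have unstable hypoglycemia for longer than 28 days". Section 4e adds: "We expect most patients to be in the study for at least a week".
- **Analysis.** Section 8 compares time-to-euglycemia by the Mann-Whitney U test. It gives no rule for an infant whose 48-hour run is incomplete when observation ends.

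**The concern.** The endpoint is a run of fixed length, so it can be established only if glucose is observed for that length of time after the last low value. The rules that end observation are written around clinical judgement and discharge, and none refers to the 48 hours. An infant can follow the plan exactly and leave with the endpoint neither reached nor ruled out.

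The analyst would then have to drop the infant, count a failure, or credit a run that nobody saw, and Section 8 does not choose among these. The call that starts the removal clock is made by clinicians who see sensor data in one arm only, so the shortfall could differ between arms. The pilot also sets out to judge whether its outcome measures are valid and to inform the sample size of a larger trial. An endpoint with unrecognised incomplete follow-up would give poor information for both.

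**Working it through.** The plan has no figure of its own to reproduce: the sample size of 10 per arm is not powered. The check is arithmetic on time windows.

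**Sensor record.** Let *d* be the hours from the last low value to the NICU team's call (not given in the documents) and *r* the hours from the call to removal (24 to 48, Section 4e). The required run is 48 hours (Section 8).

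Sensor hours after the last low = *d* + *r*

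Shortfall = max(0, 48 − *d* − *r*)

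| Removal after call, *r* (h) | Normal hours needed before call, 48 − *r* | Largest shortfall, at *d* = 0 (h) |
|---|---|---|
| 24 | 24 | 24 |
| 30 | 18 | 18 |
| 36 | 12 | 12 |
| 42 | 6 | 6 |
| 48 | 0 | 0 |

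Example with an assumed *d* of 12 and *r* of 24: 12 + 24 = 36 hours, which is 12 short. The table assumes that no low occurs after the call and that wear is not cut short by discharge. Section 4a sets no minimum tail. If monitoring or the stay ended at the call itself, *r* would be 0 and all 48 normal hours would have to come before the call.

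**Blood values after removal.** The two-a-day minimum exists to keep the sensor working, so it lapses at removal. Later samples depend on NICU practice. They can still complete the run, since euglycemia is defined on blood glucose. But the sensor-only route to detecting a low has gone, so the rest of the window is watched less closely than the first part.

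**Length of stay.** Let *S* be the stay after enrolment and *L* the time of the last low relative to enrolment (negative if before it). The run is complete at NICU exit if *S* − *L* ≥ 48.

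- Last low at enrolment (*L* = 0): stays of 24, 36 and 47 hours give runs of 24, 36 and 47 hours, all incomplete. Stays of 48, 72 and 168 hours are long enough.
- Last low 24 hours before enrolment (*L* = −24): a stay of 24 hours gives 24 + 24 = 48, just complete, if hours before enrolment count. Section 8 does not say whether they do.

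**Test.** A plain Mann-Whitney test needs a rank for every infant. Infants still unstable at day 28 could share the worst rank. An infant who leaves after a short incomplete run has no defensible rank, because the true time is known only to exceed the time observed.

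**The case against.** The strongest reply is that euglycemia is defined on blood glucose, that all blood glucose levels are recorded, and that these infants are sampled routinely. Taking the sensor off therefore does not in itself end observation. Section 4e also keeps the sensor on until the infant is on a sustainable feeding regimen and free of hypoglycemia, so many normal hours may already have passed before the call. Most infants are expected to be in the study for at least a week. This all stands, and it limits the point to what may happen in some infants. It does not supply a guarantee: no section ties the call to a number of normal hours, requires a blood sample after removal, or describes glucose collection after discharge. A long stay does not settle it either, because the sensor shortfall depends on the interval from last low to call.

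A reader might infer more than the documents support:

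- **That the endpoint cannot be observed once the sensor is off.** Blood values can complete the run, and normal hours before the call may count.
- **That infants expected to stay 24-48 hours will almost certainly lack the endpoint.** The exclusion concerns expected stay, not actual stay, and hours before enrolment may count.
- **That removal at 48 hours always gives a complete record.** Section 4a lets discharge end wear sooner, and a call that the infant can be managed at home does not mean that lows have stopped.
- **That the arms are biased in a known direction.** A difference is plausible, but nothing in the documents gives its sign or size.

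**Conclusion.** The point holds in limited form. The plan does not secure the observation that its own endpoint definition needs, Sections 4a and 4e state different removal rules, and Section 8 neither names the data source for the 48-hour run nor handles incomplete runs. The sensor shortfall is 0 to 24 hours under Section 4e. It reaches 24 hours only if removal comes at the earliest permitted time and the call coincides with the last low.

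How many infants are affected cannot be derived, because neither the interval from last low to call nor the distribution of stay is given. It may be few or none. With ten infants per arm, one such infant would be 10% of an arm, but that is not an estimate of the problem. The outcome is secondary and the study is an unpowered pilot, so this is a correction worth making rather than a threat to the trial.

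**What to change.** 1. **Reconcile Sections 4a, 4e and 8.** Study glucose observation (the sensor, masked or unmasked as assigned, together with chart blood values) should not be scheduled to end before the 48-hour window is complete while the infant remains in the NICU and in the study. This concerns data collection only. When monitoring or the stay should end is a clinical matter not judged here.
2. **Define the run in Section 8.** State whether blood values alone or blood and sensor values together decide it, whether hours before enrolment count, and that the event is dated at completion of the 48 hours, so that it is consistent with censoring at the last observation.
3. **Add a censoring rule.** Infants who leave the NICU, go home with managed hypoglycemia or reach day 28 before completing the run are right-censored at their last glucose observation.
4. **Replace the plain Mann-Whitney test for this outcome** with one prespecified rank test that handles censoring: log-rank or Gehan-Wilcoxon. The latter is the closer counterpart of the planned test.
5. **Report by arm** the number censored and the reason.

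**Cost.** A short amendment. Measured from the earliest removal under Section 4e, some infants would wear the sensor for up to about 24 hours more. At the 12-hour calibration minimum, that means about 24 / 12 = 2 calibration samples, where routine values do not already serve. In the CGM arm it also extends exposure to live readings and alarms, which can prompt further blood checks.

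**What remains.** Infants who leave early are still censored, and that censoring may be informative because the call is made with sensor data visible in one arm only. Changing the expected-stay exclusion is optional. It would give up some eligible infants and is not needed for this correction.
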